## 12.2 Clinical Laboratory Tests

Hematology, blood chemistry, and urinalysis data are collected at Screening, Day 5, Day 14, Day 28, and Day 56/Early Termination. They will be summarized by treatment group at each visit, as well as change from Baseline for continuous parameters at post-baseline visits.

- Hematology and Coagulation: hemoglobin, hematocrit, red blood cells (RBC), white blood cells (WBC) with differential, lymphocytes, monocytes, neutrophils, eosinophils, basophils, platelets, partial thromboplastin time, activated partial thromboplastin time and their change from Baseline, will be summarized by treatment group at each visit with continuous statistics (n, mean, SD, median, minimum and maximum).
- Chemistry: albumin, alkaline phosphate, alanine amino transferase, aspartate amino transferase, bicarbonate, total bilirubin, direct bilirubin, blood urea nitrogen (or urea), calcium, chloride, creatinine, lactate dehydrogenase, phosphate, inorganic, potassium, total protein, sodium, and their change from Baseline, will be summarized by treatment group at each visit with continuous statistics (n, mean, SD, median, minimum and maximum).
  - Glucose is only collected at Baseline, so there will not be any post-baseline or change from baseline summaries.
  - Creatine kinase-MB, creatinine kinase, troponin, tryptase, and chymase are only collected in special cases; they will be listed, but not summarized.
- Urinalysis:
  - Specific gravity and pH, and their change from Baseline, will be summarized by treatment group at each visit with continuous statistics (n, mean, SD, median, minimum and maximum).
  - Categorical parameters glucose, protein, blood, ketones, bilirubin, urobilinogen, nitrite, and leukocyte esterase will be summarized with counts and percentages by treatment group at each visit.
  - Urine sedimentation count (erythrocytes [RBC], leukocytes [WBC], and epithelial cells) and urine microscopy (crystals, casts, and bacteria) will be listed.

Summaries of counts and percentages of laboratory parameters that are Low, Normal, and High compared to the reference ranges will be presented by treatment at each visit and time point.

January 17, 2019

Shift tables will be presented for laboratory parameters with defined DMID grades. DMID grades are defined in Appendix 16.4, DMID Adult Toxicity Table.

All clinical laboratory results will also be listed; these listing will be sorted by subject, visit date, and lab parameter; they will also include DMID grades and the low, normal and high value flags.

Separate listings of subjects with any clinical laboratory test result outside the reference ranges will also be presented for hematology, chemistry and coagulation, and urinalysis parameters. For these listings, if a subject has a DMID grade 1 or higher value, or low and/or high flag for a parameter, or a non-normal value for a categorical urinalysis parameter, all data for that subject/parameter will be presented. These listings will be sorted by subject, parameter, then visit. An additional listing will be presented for subjects with more than a 2-grade shift in DMID grades in any lab parameter.

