10.7.4 Clinical Laboratory Tests

Actual values and changes from baseline of each continuous biochemistry, hematology, and urinalysis test will be evaluated by means of descriptive statistics by assessment time point and by treatment group. For categorical urinalysis tests, frequency tables of actual values will be provided by assessment time point and by treatment group.

Relative changes in clinical laboratory test values compared to values at baseline will be evaluated according to the DMID table (see Appendix 14.3) or in accordance with the normal ranges of the clinical laboratory (below, within, or above normal range) for parameters for which no toxicity grades are defined. A toxicity grade shift from baseline table of the abnormalities will be provided by assessment time point and by treatment group.

A listing of subjects with any clinical laboratory test result outside the reference ranges will be provided.

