% Polymorphonuclear Leucocytes + Band Cells	> 80%	90 – 95%	>95%	-----
Abnormal Fibrinogen	Low: 100-200 mg/dL High: 400-600 mg/dL	Low: <100 mg/dL High: >600 mg/dL	Low: < 50 mg/dL -----	Fibrinogen associated with gross bleeding or with disseminated coagulation
Fibrin Split Product	20-40 mcg/ mL	41-50 mcg/ mL	51-60 mcg/ mL	> 60 mcg/ mL
Prothrombin Time (PT)	1.01 - 1.25 x ULN	1.26-1.5 x ULN	1.51 -3.0 x ULN	>3 x ULN
Activated Partial Thromboplastin (APPT)	1.01 -1.66 x ULN	1.67 - 2.33 x ULN	2.34 - 3 x ULN	> 3 x ULN
Methemoglobin	5.0 - 9.9%	10.0 - 14.9%	15.0 - 19.9%	> 20.0%

CHEMISTRIES				
	Grade 1	Grade 2	Grade 3	Grade 4
Hyponatremia	130-135 mEq/ L	123-129 mEq/ L	116-122 mEq/ L	< 116 mEq/ L or abnormal sodium with mental status changes or seizures
Hypernatremia	146-150 mEq/ L	151-157 mEq/ L	158-165 mEq/ L	> 165 mEq/ L or abnormal sodium with mental status changes or seizures
Hypokalemia	3.0 - 3.4 mEq/ L	2.5 - 2.9 mEq/ L	2.0 - 2.4 mEq/ L or intensive replacement therapy or hospitalization required	< 2.0 mEq/ L or abnormal potassium with paresis, ileus or life-threatening arrhythmia
Hyperkalemia	5.6 - 6.0 mEq/ L	6.1 - 6.5 mEq/ L	6.6 - 7.0 mEq/L	> 7.0 mEq/ L or abnormal potassium with life-threatening arrhythmia
Hypoglycemia	55-64 mg/dL	40-54 mg/dL	30-39 mg/dL	<30 mg/dL or abnormal glucose with mental status changes or coma
Hyperglycemia (nonfasting and no prior diabetes)	116 - 160 mg/dL	161- 250 mg/dL	251 - 500 mg/dL	> 500 mg/dL or abnormal glucose with ketoacidosis or seizures
Hypocalcemia (corrected for albumin)	8.4 - 7.8 mg/dL	7.7 - 7.0 mg/dL	6.9 - 6.1 mg/dL	< 6.1 mg/dL or abnormal calcium with life threatening arrhythmia or tetany

CHEMISTRIES (continued)				
	Grade 1	Grade 2	Grade 3	Grade 4
Hypercalcemia (correct for albumin)	10.6 - 11.5 mg/dL	11.6-12.5 mg/dL	12.6 - 13.5 mg/dL	> 13.5 mg/dL or abnormal calcium with life threatening arrhythmia
Hypomagnesemia	1.4 - 1.2 mEq/ L	1.1 - 0.9 mEq/ L	0.8 - 0.6 mEq/ L	< 0.6 mEq/ L or abnormal magnesium with life-threatening arrhythmia
Hypophosphatemia	2.0 - 2.4 mg/dL	1.5 -1.9 mg/dL or replacement Rx required	1.0 -1.4 mg/dL intensive therapy or hospitalization required	< 1.0 mg/dL or abnormal phosphate with life-threatening arrhythmia
Hyperbilirubinemia (when accompanied by any increase in other liver function test)	1.1 - <1.25 x ULN	1.25 - <1.5 x ULN	1.5 – 1.75 x ULN	> 1.75 x ULN

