Hyperbilirubinemia (when other liver function are in the normal range)	1.1 - <1.5 x ULN	1.5 - <2.0 x ULN	2.0 – 3.0 x ULN	> 3.0 x ULN
BUN	1.25 - 2.5 x ULN	2.6 - 5 x ULN	5.1 - 10 x ULN	> 10 x ULN
Hyperuricemia (uric acid)	7.5 – 10.0 mg/dL	10.1 – 12.0 mg/dL	12.1 – 15.0 mg/dL	>15.0 mg/dL
Creatinine	1.1 - 1.5 x ULN	1.6 - 3.0 x ULN	3.1 - 6 x ULN	> 6 x ULN or dialysis required

ENZYMES				
	Grade 1	Grade 2	Grade 3	Grade 4
AST (SGOT)	1.1 - <2.0 x ULN	2.0 – <3.0 x ULN	3.0 – 8.0 x ULN	> 8 x ULN
ALT (SGPT)	1.1 - <2.0 x ULN	2.0 – <3.0 x ULN	3.0 – 8.0 x ULN	> 8 x ULN
GGT	1.1 - <2.0 x ULN	2.0 – <3.0 x ULN	3.0 – 8.0 x ULN	> 8 x ULN
Alkaline Phosphatase	1.1 - <2.0 x ULN	2.0 – <3.0 x ULN	3.0 – 8.0 x ULN	> 8 x ULN
Amylase	1.1 - 1.5 x ULN	1.6 - 2.0 x ULN	2.1 - 5.0 x ULN	> 5.1 x ULN
Lipase	1.1 - 1.5 x ULN	1.6 - 2.0 x ULN	2.1 - 5.0 x ULN	> 5.1 x ULN

URINALYSIS				
	Grade 1	Grade 2	Grade 3	Grade 4
Proteinuria	1+ or 200 mg - 1 g loss/day	2-3+ or 1- 2 g loss/day	4+ or 2-3.5 g loss/day	nephrotic syndrome or >3.5 g loss/day
Hematuria	microscopic only <10 RBC/HPF	gross, no clots >10 RBC/HPF	gross, with or without clots, OR red blood cell casts	obstructive or required transfusion

CARDIOVASCULAR				
	Grade 1	Grade 2	Grade 3	Grade 4
Cardiac Rhythm		asymptomatic, transient signs, no Rx required	recurrent/persistent; symptomatic Rx required	unstable dysrhythmia; hospitalization and treatment required
Hypertension	transient increase >20 mm/ Hg; no treatment	recurrent, chronic increase > 20mm/ Hg. /treatment required	acute treatment required; outpatient treatment or hospitalization possible	end organ damage or hospitalization required
Hypotension	transient orthostatic hypotension with heart rate increased by <20 beat/min or decreased by <10 mm Hg systolic BP, No treatment required	symptoms due to orthostatic hypotension or BP decreased by <20 mm Hg systolic; correctable with oral flu id treatment	requires IV fluids; no hospitalization required	mean arterial pressure <60mm/ Hg or end organ damage or shock; requires hospitalization and vasopressor treatment
Pericarditis	minimal effusion	mild/ moderate asymptomatic effusion, no treatment	symptomatic effusion; pain; EKG changes	tamponade; pericardiocentesis or surgery required
Hemorrhage, Blood Loss	microscopic/occult	mild, no transfusion	gross blood loss; 1-2 units transfused	massive blood loss; > 3 units transfused

RESPIRATORY				
	Grade 1	Grade 2	Grade 3	Grade 4

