## 16.4 DMID Adult Toxicity Table

### **ABBREVIATIONS: Abbreviations utilized in the Table:**

ULN = Upper Limit of Normal

LLN = Lower Limit of Normal

Rx = Therapy

Req = Required

Mod = Moderate

IV = Intravenous

ADL = Activities of Daily Living

Dec = Decreased

HEMATOLOGY				
	Grade 1	Grade 2	Grade 3	Grade 4
Hemoglobin	9.5 - 10.5 g/dL	8.0 - 9.4gm/dL	6.5 - 7.9 g/dL	< 6.5 g/dL
Absolute Neutrophil Count	1000-1500/ mm 	750-999/ mm 	500-749/ mm 	<500/ mm 
Platelets	75,000-99,999/ mm 	50,000-74,999/ mm 	20,000-49,999/ mm 	<20,000/ mm 
WBCs	11,000-13,000/mm 	13,000-15,000/mm 	15,000-30,000/ mm 	>30,000 or <1,000/mm 
% Polymorphonuclear Leucocytes + Band Cells	> 80%	90 – 95%	>95%	-----
Abnormal Fibrinogen	Low: 100-200 mg/dL  High: 400-600 mg/dL	Low: <100 mg/dL  High: >600 mg/dL	Low: < 50 mg/dL  -----	
Fibrin Split Product	20-40 mcg/ mL	41-50 mcg/ mL	51-60 mcg/ mL	> 60 mcg/ mL
Prothrombin Time (PT)	1.01 - 1.25 x ULN	1.26-1.5 x ULN	1.51 -3.0 x ULN	>3 x ULN
Activated Partial Thromboplastin (APPT)	1.01 -1.66 x ULN	1.67 - 2.33 x ULN	2.34 - 3 x ULN	> 3 x ULN
Methemoglobin	5.0 - 9.9 %	10.0 - 14.9 %	15.0 - 19.9%	> 20.0 %

January 17, 2019

CHEMISTRIES				
	Grade 1	Grade 2	Grade 3	Grade 4
Hyponatremia	130-135 mEq/ L	123-129 mEq/ L	116-122 mEq/ L	< 116 mEq/ L
Hypernatremia	146-150 mEq/ L	151-157 mEq/ L	158-165 mEq/ L	> 165 mEq/ L
Hypokalemia	3.0 - 3.4 mEq/ L	2.5 - 2.9 mEq/ L	2.0 - 2.4 mEq/ L or intensive replacement therapy or hospitalization required	< 2.0 mEq/ L
Hyperkalemia	5.6 - 6.0 mEq/ L	6.1 - 6.5 mEq/ L	6.6 - 7.0 mEq/L	> 7.0 mEq/ L
Hypoglycemia	55-64 mg/dL	40-54 mg/dL	30-39 mg/dL	<30 mg/dL
Hyperglycemia	116 - 160 mg/dL	161- 250 mg/dL	251 - 500 mg/dL	> 500 mg/dL
Hypocalcemia	8.4 - 7.8 mg/dL	7.7 - 7.0 mg/dL	6.9 - 6.1 mg/dL	< 6.1 mg/dL
Hypercalcemia	10.6 - 11.5 mg/dL	11.6-12.5 mg/dL	12.6 - 13.5 mg/dL	> 13.5 mg/dL
LS: Hypomagnesemia	1.4 - 1.2 mEq/ L	1.1 - 0.9 mEq/ L	0.8 - 0.6 mEq/ L	< 0.6 mEq/ L
Hypophosphatemia	2.0 - 2.4 mg/dL	1.5 -1.9 mg/dL or replacement Rx required	1.0 -1.4 mg/dL intensive therapy or hospitalization required	< 1.0 mg/dL
Hyperbilirubinemia	1.1 - <1.25 x ULN	1.25 - <1.5 x ULN	1.5 – 1.75 x ULN	> 1.75 x ULN
Hyperbilirubinemia	1.1 - <1.5 x ULN	1.5 - <2.0 x ULN	2.0 – 3.0 x ULN	> 3.0 x ULN

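### SAP Appendix 16.4 omits the conditions that select the bilirubin grading row and the albumin correction for calcium, leaving bilirubin grades ambiguous and some calcium grades at odds with the protocol

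*SAP*

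**What the plan says.** Protocol 10.7.4 sends laboratory grading to the DMID table in protocol Appendix 14.3. That table has two bilirubin scales. The stricter one applies "when accompanied by any increase in other liver function test"; the more lenient one applies "when other liver function are in the normal range". The protocol table labels its low-calcium row "Hypocalcemia (corrected for albumin" and asks for the same correction in the hypercalcemia row.

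SAP 12.2 presents shift tables for laboratory parameters with DMID grades and states that "DMID grades are defined in Appendix 16.4, DMID Adult Toxicity Table". In SAP Appendix 16.4 both bilirubin rows carry the bare label hyperbilirubinemia. The first begins at "1.1 - <1.25 x ULN" and nothing says when it applies. The two calcium rows carry no reference to albumin, and SAP 12.2 derives no corrected calcium.

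SAP 16.1, the list of departures from the protocol, covers the Per Protocol population, the MITT definition, the QTcF categories and the five-point ordinal scale. It does not mention laboratory grading.

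**The concern.** A grading table has to return one grade per value. With two rows under the same name and no selection rule, bilirubin does not have one, and the choice falls to whoever writes the program. Calcium is a different problem. The row can be used as printed, so the program would run without complaint and grade total calcium, which is not the protocol's rule.

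The grades feed the chemistry shift table (14.3.5.6), the graded laboratory listings and the listing of subjects whose DMID grade shifts by more than two (16.2.8.4.2). SAP 2.4 says the choice of dose for future study will be influenced by the safety profile of each dose. At about 40 subjects per arm, one reclassified subject is 1/40 = 2.5% of an arm.

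**Working it through.** The plan gives no figure to reproduce here. The check is a row-by-row comparison of protocol Appendix 14.3 with SAP Appendix 16.4, followed by grading on each rule.

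**Bilirubin.** The cut-points (x ULN) are the same in both documents. Row A is the scale the protocol uses when another liver test is raised; row B is the scale for normal liver tests.

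- Row A: Grade 1, 1.1 to <1.25; Grade 2, 1.25 to <1.5; Grade 3, 1.5 to 1.75; Grade 4, >1.75.
- Row B: Grade 1, 1.1 to <1.5; Grade 2, 1.5 to <2.0; Grade 3, 2.0 to 3.0; Grade 4, >3.0.

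| Bilirubin (x ULN) | Row A | Row B | Difference | Shift of more than 2 from Grade 0 |
|---|---|---|---|---|
| 1.1 to <1.25 | 1 | 1 | 0 | neither |
| 1.25 to <1.5 | 2 | 1 | 1 | neither |
| 1.5 to 1.75 | 3 | 2 | 1 | A only |
| >1.75 to <2.0 | 4 | 2 | 2 | A only |
| 2.0 to 3.0 | 4 | 3 | 1 | both |
| >3.0 | 4 | 4 | 0 | both |

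The rows conflict from 1.25 to 3.0 x ULN. From a Grade 0 baseline, entry to the shift listing turns on the row from 1.5 to <2.0 x ULN. For example, 1.8 x ULN is Grade 4 on row A and Grade 2 on row B.

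**Calcium.** The cut-points (mg/dL) are again the same in both documents. Hypocalcemia is Grade 1 at 8.4 to 7.8 and Grade 2 at 7.7 to 7.0. Hypercalcemia is Grade 1 at 10.6 to 11.5. Neither document gives a correction formula, so I assume

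corrected calcium = measured calcium + k x (4.0 − albumin in g/dL), with k from 0.6 to 1.0 mg/dL per g/dL.

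Measured 7.4 at albumin 2.5 (Grade 2 uncorrected):
- k = 0.6: 7.4 + 0.6 x 1.5 = 8.3, Grade 1
- k = 0.8: 7.4 + 0.8 x 1.5 = 8.6, ungraded
- k = 1.0: 7.4 + 1.0 x 1.5 = 8.9, ungraded

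Measured 10.2 at albumin 3.0 (ungraded uncorrected):
- k = 0.6: 10.2 + 0.6 x 1.0 = 10.8, Grade 1 hypercalcemia
- k = 0.8: 10.2 + 0.8 x 1.0 = 11.0, Grade 1
- k = 1.0: 10.2 + 1.0 x 1.0 = 11.2, Grade 1

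At albumin 4.0 the correction is zero and no grade changes.

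**Is it an extraction fault?** Unlikely. SAP 16.4 keeps the cut-points, the uric acid qualifier and the Grade 3 clinical clause for hypokalemia, while conditions are missing from row after row. Also gone are the Grade 4 clinical clauses for sodium, potassium, glucose, calcium, magnesium and phosphate, the dialysis clause for creatinine, and the hyperglycemia condition. The last cannot affect shifts, because SAP 12.2 says glucose is collected only at baseline.

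**The case against.** The best defense is that this is an incomplete copy of a table whose full text still stands in the protocol. A programmer who meets two rows with one name must stop and ask, and protocol 10.7.4 points to the answer. Bilirubin grading is then undefined rather than wrong, and only over part of the scale. That stands for bilirubin. It does not cover calcium, where nothing prompts the question.

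The defense is also right on several stronger conclusions that a reader might draw:

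- *That the laboratory grades and shift tables will be wrong.* Not supported. The bilirubin and calcium cut-points match the protocol's, the bilirubin rows agree below 1.25 and above 3.0 x ULN, and calcium grades move only when the correction crosses a cut-point. The documents contain no albumin data to say how often that will happen.
- *That bilirubin cases enter or leave the abnormal-value listing.* They do not. SAP 12.2 admits any DMID grade of 1 or more, or any low or high flag. Both rows start at 1.1 x ULN, and a value above ULN is flagged high anyway. Only the printed grade differs.
- *That dropping the dialysis clause corrupts the creatinine shifts because subjects on hemodialysis are eligible.* Under the protocol's clause such a subject is Grade 4 at baseline and afterwards, so shows no shift.
- *That adverse event severity is affected.* Protocol 9.2 grades events from protocol Appendix 14.3, not from SAP 16.4.

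A liver or calcium signal would also remain visible elsewhere, since SAP 12.2 summarizes values, changes from baseline and reference-range status, and lists every result.

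**Conclusion.** The point holds in limited form. SAP 16.4, as the stated definition of laboratory grades, leaves bilirubin without a single grade from 1.25 to 3.0 x ULN. The gap is two grades over >1.75 to <2.0 and one grade elsewhere in that range. From a Grade 0 baseline, the row chosen decides entry to the listing of large shifts over 1.5 to <2.0 x ULN. Calcium graded as the SAP prints it departs from the protocol's rule whenever albumin correction crosses a cut-point, and SAP 16.1 does not declare the departure.

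The bilirubin result uses only the documents' cut-points. The size of the calcium effect rests on the assumed correction of 0.6 to 1.0 mg/dL per g/dL below 4.0. The reach is the descriptive chemistry shift table and graded listings. The primary efficacy analysis, the primary safety endpoint of adverse events and serious adverse events, and the dosing-pause criteria in protocol 11.4 do not use these grades. It should be corrected, but it does not threaten the trial's main conclusions.

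**What to change.** In SAP Appendix 16.4, restore the protocol 14.3 conditions on the two bilirubin rows and the two calcium rows. Then add what the protocol itself leaves open:

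- Name the liver tests and the threshold that select the bilirubin row, for example ALT, AST or alkaline phosphatase above ULN at the same visit.
- State the albumin-correction formula, and derive corrected calcium in SAP 12.2 before grading.
- Record in SAP 16.1 any departure that is intended, including the dropped dialysis clause and the other clinical Grade 4 clauses.

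The cost for bilirubin and calcium is SAP wording and light programming. Bilirubin, ALT, AST, alkaline phosphatase, calcium and albumin are all in the chemistry panel. Dialysis status and the clinical Grade 4 conditions are not, so applying those clauses would mean linking other data. If that is not wanted, declaring the omission is enough.

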### **12.3 Vital Signs**

Vital signs heart rate, respiratory rate, temperature, systolic blood pressure, and diastolic blood pressures are recorded at Screening, on Day 1 (Baseline), Day 1 (End of Infusion), Day 3, Day 5, Day 7, Day 14, Day 28, Day 56/Early termination. During hospitalization, vital signs will be measured at the end of the infusion on Day 1 and then BID (preferably at the same time each day) up until Day 14 or discharge from the hospital if this occurs prior to Day 14.

Tables presenting vital signs will display summary statistics (n, mean, SD, median, minimum and maximum) for the observed data at each visit. The corresponding changes from Baseline at the post-baseline visits will also be presented. Temperature will be presented in degrees Celsius.

Summaries of counts and percentages of vital signs that are Not Done, Normal, Abnormal, and Abnormal - Clinically Significant will be presented by treatment at each visit and time point. Shift tables of changes from baseline will also be presented.

Summaries of counts and percentages for subjects meeting Potentially Clinically Significant (PCS) Post-Baseline Vital Sign Criteria by visit will be presented. The PCS criteria for vital signs can be referenced in Appendix 16.5. A listing of the subjects meeting PCS criteria will also be provided.

All vital signs data will be listed.

### **12.4 ECG Data**

ECGs are performed at Screening and at Day 1: End of Infusion. The heart rate, PR interval, QRS interval, QT interval, and corrected QT, using the Fridericia correction (QTcF) will be summarized; change from Baseline at the post-infusion measurement will also be summarized. The QTcF calculation will be derived within the EDC system.

Counts and percentages of subjects with QTcF interval prolongation categories of <450, >450 to ≤480, >480 to ≤500, and >500 msec, will be presented by treatment group and visit. A similar summary will be presented for subjects with QTcF increases of <30, >30 to ≤60 and >60 msec from Baseline.

January 17, 2019

A summary of normal and abnormal results, as well as shifts from Baseline for the post-infusion ECG, will be summarized with counts and percentages by treatment group.

Any clinically significant ECG findings will be collected and summarized with AEs.

All ECG data will be listed. A listing of subjects with QTcF interval prolongation of >450 to ≤480, >480 to ≤500, and >500 msec and/or QTcF increases of >30 to ≤60 and >60 msec from Baseline will be presented.

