10.7.6 Electrocardiography

The ECG variables that will be analyzed are heart rate, PR interval, QRS interval, and QT interval. Values for QT corrected for heart rate (QTc) will be derived. QTcF will be the primary correction parameter.¹³

Actual values and changes from baseline of ECG variables will be evaluated by means of descriptive statistics by assessment time point and by treatment group.

A shift from baseline table of ECG abnormalities will be provided by assessment time point and by treatment group. For absolute QTcF interval prolongation (> 450, > 480, > 500 ms) and changes from baseline (increase > 30 and > 60 ms), a frequency table by assessment time point and by treatment group will be provided.

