## 16.1 Changes to the Protocol Specified Analyses

- Due to the exploratory nature of the study, it was decided that the Per Protocol population would not be defined.
- The definition of the MITT population does not include the requirement of a post-baseline assessment of O2.
- QTcF interval prolongation categories were updated to <450, >450 to ≤480, >480 to ≤500, and >500 msec and categories for QTcF increases were updated to <30, >30 to ≤60 and >60 msec from Baseline.
- Due to the change in focus of the primary efficacy endpoint, the addition of the 5 point ordinal scale was added

January 17, 2019

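### The SAP's QTcF bands leave a value of exactly 450 msec, and an increase of exactly 30 msec, in no category

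*SAP*

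**What the plan says.** SAP section 12.4 asks for subject counts and percentages, by treatment group and visit, in "QTcF interval prolongation categories of <450, >450 to ≤480, >480 to ≤500, and >500 msec". It asks for a similar summary of "QTcF increases of <30, >30 to ≤60 and >60 msec from Baseline". The table list in SAP section 16.6.1 has the matching output, Table 14.3.5.16, by title only.

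SAP section 16.1, which records departures from the protocol's analyses, gives the same absolute bands: "QTcF interval prolongation categories were updated to <450, >450 to ≤480, >480 to ≤500, and >500 msec". The same item there restates the bands for change, also unaltered from section 12.4.

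Protocol section 10.7.6 uses one-sided thresholds instead: "For absolute QTcF interval prolongation (> 450, > 480, > 500 ms" for the absolute value and "changes from baseline (increase > 30 and > 60 ms" for change. It names no lower category.

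SAP section 12.4 also plans continuous summaries of QTcF and its change from baseline, a listing of all ECG data, and a further listing of prolonged values. That last listing begins above the thresholds: "A listing of subjects with QTcF interval prolongation of >450 to ≤480, >480 to ≤500, and >500 msec", with increases likewise starting above 30 msec.

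**The concern.** One-sided thresholds cannot leave a gap, because nobody has to be placed below the lowest one. Once they become a set of bands meant to cover everyone, each possible value needs exactly one band. The upper boundaries in the SAP meet this: 480, 500 and 60 are each closed on one side and open on the other. The lowest boundary in each set is open on both sides.

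The same bands appear in both places where the SAP states them, so a programmer who checks one against the other finds agreement rather than a prompt to query. At stake is whether the rows of a descriptive safety table account for every subject with an ECG.

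**Working it through.** **Inputs from the documents.** The SAP bands (sections 12.4 and 16.1), the protocol thresholds (section 10.7.6), about 120 evaluable subjects at 40 per arm (SAP section 2.1), and ECGs at screening and at the end of infusion on Day 1 (SAP section 12.4). The plan states no figure of its own on this point, so there is none to reproduce.

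**Step 1: do the bands cover every value?** Each whole-msec value was tested against the bands, QTcF from 300 to 700 and change from -200 to +200, counting how many bands it meets.

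| Set | Values in no band | Values in two bands |
|---|---|---|
| Absolute, as written | 450 only | none |
| Change, as written | 30 only | none |
| Absolute, lowest band ≤450 | none | none |
| Change, lowest band ≤30 | none | none |

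**Step 2: which outputs does the gap touch?** Under the protocol's strict thresholds, 450 is not above 450 and 30 is not above 30. A boundary subject therefore belongs in the lowest, non-prolonged row, and that is the only row whose count can change. One subject lost from an arm of 40 lowers that row by 1/40 = 2.5 percentage points.

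**Step 3: how often would it happen?** The documents give no QTcF mean, SD or rounding rule, so all of these are assumptions. For a normal variable recorded in whole msec, the chance of recording the value b is

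P = Φ((b + 0.5 − mean)/SD) − Φ((b − 0.5 − mean)/SD).

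The expected number of subjects is 120 × P, all arms combined, at one time point.

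| Boundary | Assumed mean | Assumed SD | P | 120 × P |
|---|---|---|---|---|
| 450 | 420 | 25 | 0.78% | 0.93 |
| 450 | 420 | 28 | 0.80% | 0.96 |
| 450 | 430 | 25 | 1.16% | 1.39 |
| 450 | 430 | 28 | 1.10% | 1.32 |
| +30 | 0 | 20 | 0.65% | 0.78 |
| +30 | 0 | 25 | 0.78% | 0.93 |
| +30 | 5 | 20 | 0.91% | 1.10 |
| +30 | 5 | 25 | 0.97% | 1.16 |

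If one decimal is kept, the interval is a tenth as wide. The expected numbers fall to about 0.09-0.14 subjects at 450 and 0.08-0.12 at +30.

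**The case against.** The best defence is that nothing of safety interest is lost. The bands that carry the signal coincide with the protocol's thresholds, and the listing of prolonged values starts at the same points, so no prolonged QTcF can be missed. A boundary value still enters the continuous summaries and the full ECG listing. There are few time points: screening and end of infusion, with a baseline repeat only if screening and baseline are more than 24 hours apart (protocol Table 1). The change table therefore has a single post-infusion column. The table is descriptive and feeds no test or decision rule. All of this stands.

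The defence can add that the frequency depends on whole-msec storage, which no section states; SAP section 12.4 says only that QTcF is derived within the EDC system. That also stands, and it could make the gap nearly empty in practice.

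Finally, the table shells are in a separate document, to be completed after the SAP text (SAP section 16.7), so how the table will be programmed cannot be seen. That is fair, but it does not rescue the text. No section assigns 450 or 30 to a band, and a programmer who closes the gap unaided departs from the stated rule, which SAP section 4.1 says is to be documented in the study report.

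A reader might go further and infer that boundary subjects vanish from QTc safety reporting, or that the prolongation percentages are wrong. The documents do not support either. Only the categorical table loses the subject. The SAP gives no denominator for it, and if that is the number of subjects with an ECG, every prolongation percentage is correct.

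**Conclusion.** The bands are wrong as written, in two places, and the consequence is small. The lowest row of one descriptive table may be undercounted, and its rows may not add up to the number assessed. The expected size is about one subject across all three arms per time point. This rests on assumed normal distributions for QTcF and its change, and on whole-msec storage; with one decimal kept it is about a tenth of that.

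The move from thresholds to bands was intended, since SAP section 16.1 records it. Nothing suggests that leaving out the two boundary values was intended: every other boundary is closed, so this reads as a drafting slip. It is a minor correction, and no conclusion about QTc prolongation depends on it.

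**What to change.** In SAP section 12.4, change the lowest absolute band from <450 to ≤450 and the lowest change band from <30 to ≤30. Make the same two changes in SAP section 16.1, and carry them into the shell for Table 14.3.5.16. The closed lower bands follow from the protocol's strict thresholds and match the way the SAP closes its other boundaries. With them, every whole-msec value tested falls in exactly one band.

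The cost is four symbols in the SAP text plus the shell. The change affects table construction only and alters no prolongation threshold.
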